### **8.5.1.2 Adverse Event's Causality with the Investigational Product**

Adverse events' causality with study drug is a clinical decision based on all available information at the moment of the adverse event onset.

Adverse reactions are classified according to the causality according to the following probabilistic categories (NOM-220-SSA1-2012):

A causality assessment would include:-

- ⊕ **Certain.** It consists of an event (clinical onset or an abnormal result of laboratory test) which occurs within a reasonable period of time following the drug's administration and which cannot be explained by the natural condition's evolution, by any concomitant pathology or by other drugs dosing. Response to drug's stop should be clearly evident.
- ⊕ **Probable.** It consists of an event (clinical onset or an abnormal result of laboratory test) which follows a reasonable period of time following the drug's administration and which can hardly be related to the natural condition's evolution, concomitant pathologies or to other drugs dosing. A clinically reasonable response is obtained upon stop of other(s) drug(s).
- ⊕ **Possible.** It consists of an event (clinical onset or an abnormal result of laboratory test) which follows a reasonable period of time following the drug's administration and which can hardly be related to the natural condition's evolution, concomitant pathologies or to other drugs dosing. There is no information available related to the suspect drug's dosing or this is not clear.
- ⊕ **Suspect.** It consists of a an event (clinical onset or abnormal laboratory test) which follows a reasonable sequence of time following the drug's dosing which makes causality unlikely (but not impossible). It might be explained in a reasonable way since it is part of the natural evolution of the condition, or it is due to the presence of concomitant pathologies or other drugs dosing.
- ⊕ **Conditional - Unclassifiable** it consists of an event (clinical onset or abnormal laboratory test result) which cannot be properly assessed since more data are required or because additional data are still being analyzed.
- ⊕ **Not evaluable - Unclassifiable** It consists of a report which suggest that there is an adverse reaction which cannot be assessed since collected information is not enough or inconsistent. The report cannot be completed or checked.

Investigators must also systematically assess the causal relationship of AEs to metformin/Gliclazide using the following definitions. Decisive factors for the assessment of causal relationship of an AE to the metformin/Gliclazide include, but may not be limited to, temporal relationship between the AE and the metformin/Gliclazide treatment, known side effects of metformin/Gliclazide, medical history, concomitant medication, course of the underlying disease, trial procedures.

- ⊕ **Unrelated:** Not reasonably related to the metformin/Gliclazide treatment. AE could not medically (pharmacologically/clinically) be attributed to the IMP/study treatment under study in this clinical trial protocol. A reasonable alternative explanation must be available.
- ⊕ **Related:** Reasonably related to the IMP/study treatment. AE could medically (pharmacologically/clinically) be attributed to the IMP/study treatment under study in this clinical trial protocol.

Other factors to be considered for adverse event's causality assessment with the study drug are:

- ⊕ Recovery or discontinuation, relapse or rechallenge: Subject's response following stopping the drug or subject's response following rechallenge should be considered based on the usual clinical course of the corresponding event.
- ⊕ Response pattern known for this type of drug: Clinical/Pre-clinical
- ⊕ Exposure to physical and/or mental stress: Exposure to stress may produce adverse changes in the receptor and provide a rationale and a better explanation for the event.

Test drug's pharmacology and pharmacokinetics: Test drug's pharmacokinetic properties (absorption, distribution, metabolism and excretion) as well as the subject's individual pharmacodynamics should be considered.

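### In the six-class causality scale, Possible repeats the condition for Probable and Probable rests on stopping other drugs, so a documented event with two plausible causes has no class above Suspect

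*Protocol*

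**What the plan says.** Protocol section 8.5.1.2 asks for causality on two scales.

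The first has six classes and cites NOM-220-SSA1-2012. The wording that matters is:

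- Certain: other causes cannot explain the event, and "Response to drug's stop should be clearly evident".
- Probable: the event "can hardly be related to the natural condition's evolution, concomitant pathologies or to other drugs dosing. A clinically reasonable response is obtained", and the sentence continues so that the response follows stopping other drugs.
- Possible: the event "can hardly be related to the natural condition's evolution, concomitant pathologies or to other drugs dosing. There is no information available". The full second sentence reads "There is no information available related to the suspect drug's dosing or this is not clear".
- Suspect: the time sequence is one "which makes causality unlikely (but not impossible). It might be explained in a reasonable way since it is part of the natural evolution"; other illness and other medicines also count as explanations.
- Two unclassifiable classes, for data that are pending, insufficient or inconsistent.

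The second scale is binary and is required in addition. Related is defined as "Reasonably related to the IMP/study treatment", explained as an event for which attribution to the treatment is medically possible. Unrelated needs the opposite, together with a reasonable alternative explanation. The same section then lists further factors to weigh, among them how the subject responds once the drug is stopped.

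**The concern.** A graded causality scale works only if each step down relaxes a condition. Here the step from Probable to Possible does not relax the condition on other causes. The next class down already treats the drug as an unlikely cause. The ordinary intermediate case, where the drug may have caused the event but something else may have too, has no class of its own.

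The sentence on stopping a drug in Probable is a separate fault. Recovery after another drug is stopped points to that other drug, so it is not support for the study drug.

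At stake is whether the six-class causality recorded for an event means what its label suggests. Safety and tolerability in the fed and fasted states is a secondary objective (protocol section 5.2), and section 8.5.1.10 sends adverse reactions to the national centre under the same standard. A causality class with a faulty definition would carry into any summary or report that uses it.

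**Working it through.** No figure in the plan bears on this point and no arithmetic applies. The check sets the definitions side by side and then runs one event through them.

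**Step 1. Conditions by class (protocol section 8.5.1.2, paraphrased).**

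| Class | Other causes | Further condition |
|---|---|---|
| Certain | cannot explain the event | clear response to stopping the drug |
| Probable | can hardly explain it | response to stopping other drugs |
| Possible | can hardly explain it (same words) | dosing information on the suspect drug absent or unclear |
| Suspect | may reasonably explain it | causality described as unlikely, though not excluded |
| Conditional | none stated | more data needed or still under analysis |
| Not evaluable | none stated | information insufficient or inconsistent |

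Probable and Possible share the whole of the second column. They differ only in the third.

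**Step 2. A test event.** Take nausea soon after dosing in a subject who also has a mild intercurrent gastroenteritis, with timing, dose and course fully recorded. The example is hypothetical. Protocol section 4 lists nausea among the very common gastrointestinal reactions to the combination, so a drug cause is plausible; so is the infection.

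- Certain fails, because another cause can explain the event.
- Probable fails, because the other cause is plausible.
- Possible fails on the same clause. It would also fail on the dosing clause, since section 7.9 has dose, full intake and time checked and recorded.
- Suspect is the only class whose condition on other causes is met. It also describes causality as unlikely, which is not the assessor's view of this event. Read strictly, Suspect does not fit either.
- Conditional and Not evaluable do not apply, because the data are complete and consistent.

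The event goes to Suspect or to no class.

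**Step 3. The same event on the binary scale.** Related asks only whether the event could medically be put down to the treatment, and sets no condition on other causes. The event is Related.

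**Step 4. The sentence on stopping a drug.** Certain refers to stopping the drug, and the later factor list in the section also refers to the drug. Probable alone says "A clinically reasonable response is obtained upon stop of other(s) drug(s". Section 7.5.1 generally does not allow concomitant drugs, so there will usually be no other drug to stop and the condition can seldom be met.

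**Step 5. Where the six-class result is used.**

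- Section 8.5.1.10 requires serious events to be notified within 24 hours, whatever their class.
- Section 8.5.1.11 sends all serious and non-serious events to the committees and health authorities. It describes SUSARs in terms of relatedness to the product, which is the language of the binary scale, although it does not name a scale.
- Section 9.5 plans descriptive summaries of adverse events. Neither document specifies a table by causality class, and the SAP, just before its reference list, leaves the clinical results to the clinical report.

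**The case against.** The strongest reply is that little depends on the six classes. The binary scale is mandatory, and its Related is broad enough to capture the test event. Serious events are reported regardless of class. The section opens by making causality a clinical judgement on all available information, and it later names the correct factor, the response to stopping the drug. The subjects are screened healthy volunteers who generally may not take other drugs, so competing causes may be few. Each exposure is a single tablet, so there is normally no continuing treatment to stop, and correcting the sentence in Probable would change little in practice.

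Most of this stands, and it limits the consequence. It does not repair the definitions: an assessor who applies them as written still has nowhere suitable to put the test event.

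Three stronger readings are tempting and are not supported.

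- A reader might infer that related serious events could escape SUSAR identification. The wording of section 8.5.1.11 follows the binary scale, on which such an event is Related.
- A reader might infer that the fed versus fasted tolerability comparison is distorted. The same definitions apply in both states, total event counts do not depend on causality class, and no comparison by class is planned.
- A reader might infer that the two scales give opposite answers. Suspect says "which makes causality unlikely (but not impossible"), and Related needs only that attribution is possible. The pair is awkward but not a strict contradiction.

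A full table translating one scale into the other would be tidy. Its absence is a matter of preference and not an error.

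**Conclusion.** The point holds as a fault in the operative definitions. Possible does not admit a plausible alternative cause, Probable refers to stopping the wrong drug, and a fully documented event with two plausible causes is left to Suspect or to no class while the binary scale calls it Related.

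The effect is confined to the six-class causality record and to any safety summary or report that draws on it. Serious-event reporting, overall adverse event counts by fed or fasted state, SUSAR capture through the binary scale and the primary pharmacokinetic analysis are not shown to be affected. The number of events concerned cannot be estimated from the documents.

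The conclusion rests on the protocol's own wording. The text of NOM-220-SSA1-2012 is not available here, so whether the fault is one of translation or copying, or lies in the source, cannot be judged.

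**What to change.** In protocol section 8.5.1.2:

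1. Correct Possible so that it covers an event with a reasonable time sequence that may also be explained by the natural course, other pathology or other drugs.
2. Correct the sentence in Probable so that the response refers to stopping the suspect (study) drug, in line with Certain and the later factor list.
3. Check both sentences against the cited NOM-220-SSA1-2012 text before adopting them, so that the correction does not create a new mismatch with the standard.
4. State which of the two scales governs safety summaries and SUSAR assessment.

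The cost is wording in the protocol and in the matching CRF completion instructions. No new data, visits or staff are needed.

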### **8.5.1.3 Adverse Event Severity**

Adverse events intensity or severity should be classified as follows (NOM-220-SSA1-2012):

- ⊕ Mild  
They occur with easily tolerated signs and symptoms. They do not require treatment or extend hospitalization, and do not necessarily require drug's discontinuation.
- ⊕ Moderate  
They interfere with usual activities (may cause work or school absenteeism) without affecting patient's life directly. They require pharmacological therapy and do not necessarily require the discontinuation of the drug which caused the event, reaction, or suspect adverse reaction.
- ⊕ Severe  
They interfere with usual activities (may cause work or school absenteeism). They require pharmacological therapy and the discontinuation of the drug which caused the event, reaction, or suspect reaction.

### **8.5.1.4 Laboratory Abnormal Findings**

Abnormal laboratory findings and other abnormal findings during the study (e.g., ECG trace) should not be reported as serious adverse events, unless they are related to clinical signs and symptoms, which cause treatment's discontinuation or, in the other hand, they are considered clinically important by the Principal Investigator. In the event laboratory abnormality meets these criteria, the identified medical condition (for instance, anemia, and high ALT) should be reported as an adverse event instead of the abnormal value by itself.

### **8.5.1.5      Unexpected Adverse Event**

An unexpected adverse event is any adverse event which specificity or severity is not mentioned in the most recent product's information (Investigator's Brochure - or package insert for marketed products). Likewise, reports which provide important information about specificity or severity of a known adverse event, already documented, constitute unexpected adverse events. For instance, any event which is more specific or more severe than those described in the Investigator's Brochure should be considered "unexpected".

### **8.5.1.6      Adverse Events of Special Interest**

Hypoglycemia is a condition characterized by abnormally low blood glucose levels, usually less than 70 mg/dl and may be associated with the following symptoms: headache, increase appetite, nausea, vomit, tiredness, drowsiness, sleep disorders, restlessness, aggressiveness, reduced concentration, wakefulness and reaction; depression, confusion; visual and speech disorders; aphasia; tremors, paresis, sensory disorders, dizziness, helplessness feeling, lack of self-control, delirium, seizures, shallow breathing, bradycardia, drowsiness, syncope which might lead to coma and death.

Subjects will be monitored closely in the event of a nonserious AESI, the investigator will complete the AESI Report Form and send it to the Sponsor. Names, addresses, and telephone and fax numbers for AESI reporting will be included on the Report Form. Serious AESIs have to be reported in an expedited manner as SAEs as outlined above.

### **8.5.1.7      Serious Adverse Event**

A serious adverse event is any unexpected medical occurrence which at any dose:

- Results in death.
- It is life-threatening.
- Requires hospitalization or prolongs the existing hospitalization.
- Results in persistent or important disability or incapacity.
- It is a congenital abnormality or birth defect.
- It is a clinically important event.

Some clinically important events, although they do not lead to death, are not life-threatening or require hospitalization, may be considered serious adverse events based on the appropriate medical judgment and the need of medical or surgical care to avoid the events previously mentioned in this definition. Examples of those medical events include: allergic bronchospasm which require intensive care in the emergency room or at home, blood dyscrasias or seizures which require hospitalization, or the development of drug's dependence or abuse.

Life-threatening means that the subject was in danger, as per Investigator's judgment, immediate risk of death due to the reaction when it occurred.

Disability means an important disorder in the capacity of a person to perform usual functions or activities.

For reporting purposes, any suspect of transmission of an infective agent by any of the study drugs is considered a serious adverse event, as described in section 8.5.1.4.

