#### **4 Adverse Reactions of the combination product (Metformin/Gliclazide)**

##### **Hypoglycemia**

As for other sulphonylureas, treatment with Gliclazide can cause hypoglycemia, if mealtimes are irregular and, in particular, if meals are skipped. Possible symptoms of hypoglycemia are: headache, intense hunger, nausea, vomiting, lassitude, sleep disorders, agitation, aggression, poor concentration, reduced awareness and slowed reactions, depression, confusion, visual and speech disorders, aphasia tremor, paresis, sensory disorders, dizziness, feeling of powerlessness, loss of self-control, delirium, convulsions, shallow respiration, bradycardia, drowsiness and loss of consciousness, possibly resulting in coma and lethal outcome.

In addition, signs of adrenergic counter-regulation may be observed: sweating, clammy skin, anxiety, tachycardia, hypertension, palpitations, angina pectoris and cardiac arrhythmia.

Usually, symptoms disappear after intake of carbohydrates (sugar). However, artificial sweeteners have no effect. Experience with other sulphonylureas shows that hypoglycemia can recur even when measures prove effective initially. If a hypoglycemic episode is severe or prolonged, and even if it is temporarily controlled by intake of sugar, immediate medical treatment or even hospitalization is required.

Blood and lymphatic system disorders

Rare: Hematologic disturbances which may include anemia, leucopenia, thrombocytopenia, granulocytopenia. These are in general reversible upon discontinuation of medication.

Metabolism and nutrition disorders

Very rare: Lactic acidosis. Decrease of vitamin B12 absorption with decrease of serum levels during long-term use of Gliclazide. Consideration of such etiology is recommended if a patient presents with megaloblastic anemia.

Frequency not known: Hypoglycemia.

Nervous system disorders

Common: Taste disturbance.

Eye disorders Frequency not known: Transient visual disturbances may occur especially on initiation of treatment, due to changes in blood glucose levels. Gastrointestinal disorders

Very common: Gastrointestinal disorders such as nausea, vomiting, diarrhea, abdominal pain, and loss of appetite.

Frequency not known: Constipation and dyspepsia.

These undesirable effects can be avoided or minimized if dose is increased slowly and Gliclazide is taken with breakfast.

Hepatobiliary disorders

Very rare: Liver function tests abnormalities or hepatitis resolving upon treatment discontinuation.

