## **8.5.1 Adverse Event**

### **8.5.1.1 Adverse Event Definitions**

#### **Adverse Event**

An adverse event is any untoward medical occurrence which may occur during drug's clinical research stage but which do not necessarily has a causal relation with the drug. Therefore, an adverse event can be any untoward sign and symptom (including any abnormal finding in the laboratory tests), or condition temporarily related to the use of the drug (investigational), whether related or not to that product.

Adverse events associated to the use of drugs in humans, related or not to the drug, include the following:

- ✚ Any adverse event occurring during the use of the drug in the professional practice.
- ✚ An adverse event which occurs because of the abuse of drug products or substances.
- ✚ An adverse event which occur following the stop of drug's intake.
- ✚ An adverse event where there is a reasonable possibility that the event occurred only as a consequence of the subject's participation in the study (e.g., adverse event or serious adverse event due to the stop of anti-hypertensive drugs during wash-out phase) should be reported as an adverse event even though this is not related to the investigational product.
- ✚ Clinical onset on any failure of the expected pharmacological action.

In case the event meets the criteria for "serious" adverse event, it should be recorded and reported as that.

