### **8.5.1.11 Report of Safety Information to the Health Authorities, Ethics and Investigation Committee and Investigational Committee**

According to local law and regulation, all serious and non-serious adverse events should be reported to the appropriate Ethics and Investigation Committee, Investigational Committee and to the Health Authorities. This will be carried out according to the standard operating procedure, code: PPD [REDACTED], REPORT OF CLINICAL AND BIOAVAILABILITY STUDIES ADVERSE EVENTS

The Investigator must comply with any applicable site-specific requirements related to the reporting of SAEs (particularly deaths) involving trial subjects to the IEC/IRB that approved the trial.

In accordance with ICH GCP, the Sponsor/designee will inform the Investigator of “findings that could adversely affect the safety of subjects, impact the conduct of the trial or alter the

IEC’s/IRB’s approval/favorable opinion to continue the trial.” In particular and in line with respective regulations, the Sponsor/designee will inform the Investigator of AEs that are both serious and unexpected and are considered to be related to the administered product (“suspected unexpected serious adverse reactions” or SUSARs). The Investigator should place copies of Safety Reports in the Investigator Site File. National regulations with regard to Safety Report notifications to Investigators will be taken into account.

When specifically required by regulations and guidelines, the Sponsor/designee will provide appropriate Safety Reports directly to the concerned lead IEC/IRB and will maintain records of these notifications. When direct reporting is not clearly defined by national or site-specific regulations, the Investigator will be responsible for promptly notifying the concerned IEC/IRB of any Safety Reports provided by the Sponsor/designee and of filing copies of all related correspondence in the Investigator Site File.

For trials covered by the European Directive 2001/20/EC, the Sponsor’s responsibilities regarding the reporting of SAEs/SUSARs/Safety Issues will be carried out in accordance with that Directive and with the related Detailed Guidance documents.

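### The serious adverse event definition uses *unexpected* where *untoward* is needed, so it can be read as excluding serious reactions that are already listed

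*Protocol*

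**What the plan says.** Protocol Section 8.5.1.7 defines the serious adverse event (SAE): "A serious adverse event is any unexpected medical occurrence which at any dose", and then lists death, threat to life, hospitalisation, disability, congenital abnormality and clinically important events.

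Section 8.5.1.5, under its own heading, defines the qualifying word: "An unexpected adverse event is any adverse event which specificity or severity is not mentioned in the most recent product's information". The Investigator's Brochure or package insert is the reference. An event more specific or more severe than the Brochure describes also counts as unexpected.

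Section 8.5.1.1 uses a different word for the general term: "An adverse event is any untoward medical occurrence which may occur during drug's clinical research stage".

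Section 8.5.1.11 describes suspected unexpected serious adverse reactions (SUSARs) as "AEs that are both serious and unexpected and are considered to be related to the administered product".

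Section 8.5.1.10 contains two 24-hour rules. One covers SAEs and suspected serious adverse reactions, and goes to the national pharmacovigilance centre and the sponsor. The other requires a written report of any new SAE to the sponsor on the SAE Report Form.

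**The concern.** Seriousness describes the outcome of an event. Expectedness describes whether the event is already documented. The first line of Section 8.5.1.7 makes the first depend on the second, using a word that the protocol has defined only two sections earlier.

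An investigator who applies both definitions literally could decide that a known reaction leading to hospital admission is not an SAE, because the product information already describes it. Another investigator, looking only at the seriousness criteria, would call it one. The SAE label triggers the written 24-hour form to the sponsor and is also a listed reason for withdrawal (Section 6.3.3, item 5). The same event could therefore be handled in two ways, and the text would support either.

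**Working it through.** No arithmetic applies. The check sets the sections side by side.

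**Step 1: the literal definition.**
- SAE = unexpected AND at least one seriousness criterion (Section 8.5.1.7).
- Unexpected = not in the product information, or more specific or more severe than described there (Section 8.5.1.5).
- Hence a reaction that is serious, but already listed at that nature and severity, fails the first condition.

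**Step 2: is there a concrete case?** Lactic acidosis appears among the metformin reactions in Section 3.1.8 and among those of the combination in Section 4: "Very rare: Lactic acidosis". Section 7.11, in its overdose text, calls the condition an emergency needing hospital treatment, which points to the hospitalisation criterion. It would be serious and, if the product information matches the protocol's lists, expected. On the literal reading it is not an SAE.

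**Step 3: does the rest of the protocol follow the restriction?**

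| Protocol section | What it does | Fits the restriction? |
|---|---|---|
| 8.5.1.1 | Defines an adverse event as *untoward* | No |
| 8.5.1.6 | Sends serious hypoglycaemia, a known reaction, through SAE reporting | No |
| 8.5.1.7, examples | Names blood dyscrasias and seizures leading to admission, although Sections 3.2.8 and 4 list haematological disorders and seizures or convulsions as known | No |
| 8.5.1.10 | Distinguishes expected from unexpected when it deals with mild and moderate reactions | Uses the word in its technical sense |
| 8.5.1.11 | Treats serious and unexpected as two separate attributes | No: the second would be redundant if every SAE were unexpected |

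The first line of Section 8.5.1.7 is the outlier.

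**Step 4: what would still catch a listed serious reaction?**
- Section 8.5.1.1 says that an event meeting the criteria for a serious adverse event is to be recorded and reported as one. This helps if *criteria* means the seriousness list. It is circular if it means the whole of Section 8.5.1.7.
- The first 24-hour rule in Section 8.5.1.10 also covers suspected serious adverse reactions. Hospital-treated lactic acidosis attributed to the drug would naturally fall there. The rule for the SAE Report Form names only SAEs.
- Section 8.5.1.11 sends all adverse events, serious or not, to the committees and health authorities.
- Section 8.5.1.8 requires every adverse event to be recorded in the case report form.

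Such an event would therefore be recorded and would probably reach the authority. What stays open is its classification as an SAE, and with it the written form to the sponsor.

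**The case against.** The strongest reply is that this is a word slip. The term defined in Section 8.5.1.5 is an unexpected *adverse event*, whereas Section 8.5.1.7 speaks of an unexpected *medical occurrence*, which parallels the *untoward* phrase in Section 8.5.1.1. The protocol reads as a translation: a Spanish *y* survives in the model notation of Section 9.5. A sensible investigator would apply the seriousness criteria, and the neighbouring sections point that way. As an account of intent this is persuasive. It does not make the definition correct, because the intended meaning is reached only by overriding the operative sentence with other sections.

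The reply also defeats four stronger inferences that a reader might draw:

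- **That every listed reaction falls outside the SAE definition.** Section 8.5.1.5 still counts a case more severe or more specific than described as unexpected. Section 4 describes hepatitis as resolving once treatment stops and blood changes as generally reversible, so a fatal or disabling case could still qualify.
- **That serious hypoglycaemia is the only known reaction brought back in.** The examples in Section 8.5.1.7 also name blood dyscrasias and seizures.
- **That all 24-hour reporting depends on this definition.** The rule for suspected serious adverse reactions in Section 8.5.1.10 is a second route.
- **That serious events in the fed and fasted comparison would be under-counted.** Every adverse event goes into the case report form, and Section 9.5 plans descriptive summaries of adverse events. A mislabelled event would still appear in them.

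**Conclusion.** The point holds as a contradiction in an operative safety definition. As written, Section 8.5.1.7 can be read as excluding serious reactions already listed at the same nature and severity, and it conflicts with Sections 8.5.1.1, 8.5.1.6 and 8.5.1.11 and with its own examples. The consequence is possible inconsistency in SAE classification and in 24-hour reporting on the SAE form. The documents do not support a conclusion that such events would go unreported, and they do not show that any event was missed.

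The practical size is small: 22 healthy volunteers receive two supervised single doses. Sample size and the pharmacokinetic analysis are untouched.

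One assumption matters. Expectedness is judged against the Investigator's Brochure or package insert, which is not among the documents. That lactic acidosis is listed there is inferred from the reaction lists in Sections 3.1.8 and 4. The conflict in wording does not depend on that inference; the example does.

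**What to change.** In the first line of Section 8.5.1.7, replace *unexpected* by *untoward*, matching Section 8.5.1.1, so that seriousness does not depend on expectedness. Keep *unexpected* for Section 8.5.1.5 and for the expectedness and SUSAR reporting text in Sections 8.5.1.10 and 8.5.1.11.

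Section 8 of the SAP describes the trial as already run (22 randomised, 21 finished). The clinical report should therefore also state that events were classified on the seriousness criteria alone, whether or not the reaction was listed.

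The cost is one word in the protocol and a short check of the adverse event records. No analysis changes.
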